8.0 Data Collection and Management Procedures

- Data will be collected by the PI, Co-I or an authorized member of the research team and coded to the study number assigned to each subject. All electronic data will be secured on the PIs encrypted and password protected computer until it can be moved to a secure UIC data server for long-term storage. Hard copy data reporting forms will be stored in a locked file cabinet until it can be scanned to electronic copy and archived onto the UIC data server. Once files are converted the original hard copy will be kept until the study is closed, at which time the documents will be destroyed. In the event that a discrepancy or error is found in the source data, the PI will determine if the data can be collected again/procedure repeated in a subsequent study visit or alternative visit provided this will not disrupt the integrity of the data. Should this occur, the event will be documented and reported to the IRB. Access to the data will be limited to the PI and IRB-authorized members of his research team. The PI will examine safety and review all data on an ongoing basis. Source data will be collected in data reporting forms of both electronic and written form. The PI will review these forms and data at the completion of each subject visit to ensure both accuracy and completeness.

9.0 Data Analysis

- Data will be analyzed according to the plan for statistical analysis presented below.

10.0 Quality Control and Quality Assurance

- The PI will evaluate the data for adherence with the protocol and for accuracy in relation to source documents.
- The PI is responsible for the evaluation of data quality and will review the data in an ongoing basis.

11.0 Data and Safety Monitoring

- The IRB will be responsible for human subject protection oversight through annual periodic review of research involving human subjects. All personnel participating in research

activities will meet UIC and OHRP IRB requirements for human subjects research, including completion of an approved CITI human subjects training (or institutional equivalent) and refresher courses at required intervals.

- Each year, the PI will submit a progress report to the UIC IRB, which will review progress and re-approve the protocol. As part of these reviews, the PI will report how many subjects have been recruited, the outcomes to date and if there have or have not been any non-serious adverse reactions reported by the study participants.
- Various aspects of the study will be monitored as follows: data quality, subject recruitment, accrual and retention, adverse events, assessment of scientific reports or therapeutic development, results of related studies that impact subject safety, and procedures designed to protect the privacy of subjects.
- A **Data and Safety Monitoring Board (DSMB)** will monitor human subject safety, protocol compliance and data integrity. The DSMB will consist of three experienced physicians / nurses who as a group have a good clinical and investigative understanding of the study protocol based on their backgrounds ([name], Assistant Professor of Clinical Medicine, Division of Endocrinology and Metabolism; [name], Associate Professor of Clinical Obstetrics and Gynecology; and [name], Professor of Nursing). The DSMB will be chaired by [name] who has an excellent knowledge base of endocrine and metabolic research and DSMB oversight. [name] will also be the medical safety monitor. DSMB members will not be directly involved in the study.

Initial Meeting: The DSMB will meet prior to initiation of the study to review the protocol, resolve queries, and approve the research protocol and informed consent document.

Interim Meetings: In open session, the DSMB will meet at least twice a year to review the ongoing recruitment process, participant withdrawal and protocol deviations. It will review any study protocol amendments and follow the continuing review process. It will review participant safety and discuss any serious adverse events that may occur, including the relationship of adverse events to study intervention. It will review the study protocol to determine if any protocol revisions are merited as suggested by interim results, adverse events, or external events such as new FDA recommendations. It will review the informed consent document and confirm consistency with risks of participation to determine if any consent document revisions are merited. It will discuss any issues raised by the clinical study team. At the conclusion of each meeting, one of the following dispositions will be recommended: continue the study without changes, continue the study with specified changes, place the study on Clinical Hold pending further discussion or investigation, or terminate the study.

Key Features to be Assessed: Monthly salicylate levels measured at Visits 1, 6, 7 and 8 by Labcorp Clinical Laboratories will eventually be used to assess compliance after the study is unblinded upon its completion to accurately interpret the study data, but will not be used for clinical management. To avoid blinding bias, the monthly salicylate levels will not be posted in a subject's electronic medical record. Instead, DSMB members under [name] direction will prospectively receive copies of these salicylate levels for safekeeping. Development of tinnitus during salsalate use will be used to assess salicylate toxicity clinically as in a previous large multicenter trial.¹⁹ As an additional precaution, salsalate will be prepared as 500 mg capsules and identical placebo capsules so the blinding will not be jeopardized when changing the dose in one capsule increments to manage tinnitus.

Operating Procedures: The DSMB will convene after 5 participants have completed the study protocol or 6 months following completion of the first participant (whichever occurs first); and thereafter at least twice a year. If there is a concern about serious adverse events, more frequent meetings may be called by vote. If unexpected and/or serious adverse events occur disproportionately to what may be anticipated, the study will be placed on clinical hold and the IRB will be consulted for guidance.

Minutes will be taken by the Research Nurse Study Coordinator and forwarded to the DSMB chair for review. The final version of the minutes will be sent to all DSMB members for approval. A formal report from the chair, following approval by the DSMB members will be supplied to the IRB within six weeks of each meeting. Each report will conclude with a recommendation selecting one of the following dispositions: continue the study without changes, continue the study with specified changes, place the study on clinical hold pending further discussion or investigation, or terminate the study. In the case of clinical hold or study termination, the report will be disseminated to the research team as rapidly as possible.

Interim Reporting: The PI will provide Interim data reports to the DSMB. Types of reports for each meeting include summaries of the following: baseline clinical and demographic characteristics of study participants, the recruitment process, including numbers screened, numbers enrolled, withdrawals, adherence and deviation from the study protocol. Any adverse events, including serious, study-related adverse events, will be evaluated by the DSMB. In particular, they will be concerned with adverse events that may affect continued study participation. Specific items to be reported will include: tinnitus during study medication treatment, hypoglycemia during an OGTT or FS-IVGTT, allergic reactions to study medications or any other serious adverse events.

- Anticipated risks/adverse events noted in the consent form will be handled as follows:

| Risks and/or Anticipated Adverse Events | Assessment Measures | Individual doing Assessment | Assessment Intervals or Frequency | Interventions to Decrease or Respond to Risks |
|---|---------------------------------------|------------------------------------|-----------------------------------|---|
| Venipuncture DEXA scans | Patient observation | CRC Staff | During the procedure | Verbal explanation; Provide privacy; Performed by qualified, trained personnel. |
| Venous access and blood draws | Patient observation | CRC R.N. | During the procedure | Performed by M.D. or R.N.; Provide complete explanation and expectations before the procedure, both verbally and in the consent form. |
| Pain | Patient observation and communication | CRC R.N. | During the procedure | Tylenol as ordered; Explain procedure and rationale to patient. |

| | | | | |
|---|---|---|---|--|
| Infection | Patient observation and vital signs | CRC R.N. | During the procedure | Blood draws performed under sterile technique; Instruct patient regarding infection signs and symptoms and importance of reporting these to the M.D.; Provide M.D. and CRC telephone number in the event of a problem. |
| Bleeding, bruising or anemia | Patient observation and communication | CRC R.N. | During procedure | Careful closure of stopcocks between blood draws; Meet hemoglobin IRB requirements. |
| Thrombosis | Observe blood flow during draws | CRC R.N. | Every blood draw to check patency of lines. | 0.9% NS infusion @ 30cc/hr throughout the test. |
| Hypoglycemia during FS-IVGTT infusion of insulin. | Patient observation and frequent glucose measurements | CRC R.N. and Research Nurse Study Coordinator | Every 1-10 minutes during the initial 1½ hours of the FS-IVGTT starting 20 minutes before the test, then every 20-30 minutes for the next 1½ hours. | Cessation of the infusions and intravenous glucose administration if patient becomes symptomatic (i.e. headache, shakiness, visual changes and palpitations) or glucose level falls below 70 mg/dl. |

- A participant will be monitored continuously during an entire CRC visit to undergo study procedures, and the PI will be present within the hospital and available by telephone, pager or e-mail throughout each visit. In the situation of an anticipated or an unanticipated Adverse Event (AE), a standard IRB Adverse Event Report Form will be sent to the CRC and IRB in a timely manner. This report will include a full description of the event, including the relationship of the AE as not related, possibly related, or definitely related to the study procedure. The PI, in consultation with the DSMB, will grade adverse events severity as follows (as recommended by the National Cancer Institute):

- 0 – “No adverse event or within normal limits or not clinically significant”
- 1 – “Mild AE, did not require treatment”
- 2 – “Moderate AE, resolved with treatment”
- 3 – “Severe AE, resulted in inability to carry on normal activities and required

- professional medical attention”
- 4 – “Life threatening or disabling AE”
- 5 – “Fatal AE”

- A participant's study will be stopped in the event she requests not to continue, or if she has a reaction to any procedure, the ingestion of the glucose beverage during the OGTT, the HCG injection, dairy cream ingestion during the CCT, difficulty obtaining a peripheral intravenous line, administration of salsalate (i.e. allergies, persistent or serious side effects, unusual anxiety). The participant's treating physician will attend to any serious adverse events that may occur until they have resolved or refer the participant to the appropriate provider as needed. A participant will also be asked to stop the study if she is not compliant with the requirements of the study protocol. All participants will be assessed for side effects at the end of the study. Study discussions will be documented within each participant's study binder. Follow-up with the IRB or CCTS CRC will also be noted, and copies will be kept of all correspondence.
- If a participant withdraws from the study, she will be replaced by a different participant to achieve accrual of 90 participants to complete the study. Additional reasons for withdrawal may include but are not limited to a family emergency, a new medical diagnosis, participant preference or development of any persistent study medication side effects that do not resolve with common clinical measures in a timely fashion. The IRB and CCTS CRC will be notified during an annual continuing review of subject accrual to date, and any withdrawals or dropouts.
- If a serious adverse event occurs during the study, the PI will promptly report the event to the IRB (in accordance with UIC OPRS Prompt Reporting policy) and to the study DSMB for review and possible action. In the unlikely event of any serious adverse reactions occurring during this study, the DSMB will also provide appropriate clinical expertise for advice and assistance. The study will be completely suspended in the event of death of a subject.
- The PI will keep abreast of scientific reports or therapeutic development, and results of related studies that impact subject safety; and will inform subjects immediately of new information from these reports or studies that change the risk/benefit ratio for study participation. This type of information will also be reported to the DSMB and to the IRB during an annual continuing review.

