- **Insulin-Modified FS-IVGTT:** The test will be performed in the CRC two (2) days after the CCT after an overnight fast of ~12 hours as described by Polidori et al.³² An intravenous polyethylene catheter will be inserted in an forearm vein at ~7:10 AM (-50 minutes) for infusing glucose and insulin. Another intravenous catheter will be inserted in a contralateral forearm vein for blood sampling. The size of the catheter (i.e. 18-23-gauge) will be of suitable caliber for the size of the vein used to gain access (*please refer to the Risks - Venipuncture / Venous Catheter Blood Sampling subsection of Section 7.0 for the approach and alternatives to intravenous catheter placement*). Baseline blood samples will be obtained at ~7:40 AM (-20 minutes), ~7:50 AM (-10 minutes), ~7:59 AM (-1 minute) and ~8 AM (0 minutes). The average of the four samples is considered the basal level. A glucose solution (0.3 gm/kg) will be administered intravenously beginning immediately after the 0 minute blood draw. Insulin (20 mU/kg Humulin; Eli Lilly, Indianapolis, IN) delivered in 1 unit/ml infused over 60 seconds starting at ~8:20 AM (20 minutes). Blood samples will be obtained at -20, -10, -1, 0, 1, 2, 3, 4, 5, 6, 7, 8, 10, 12, 14, 16, 19, 22, 23, 24, 25, 27, 30, 40, 50, 60, 70, 80, 90, 100, 120, 150, 180 and 240 minutes. Every attempt will be made to insert the intravenous catheters and obtain blood samples on time. However, all samples with the exception of those used to measure glucose may be obtained within a fifteen minute window after the scheduled time due to any unforeseen technical difficulty. A total of 272 ml of blood (8 ml/sample) will be collected during the entire procedure. All infusions will be stopped at 12 PM. Upon completion of the test, both catheters will be removed, and subjects will be fed a standard lunch. Plasma will be isolated from the blood samples collected and stored at -80° C until assayed for glucose, insulin, C-peptide and FFA. Preparation of glucose and insulin for infusion during the FS-IVGTT procedure will be performed by the UI Hospital Pharmacy Investigational Drug Services.

- *Mathematical Model to Assess Hepatic and Extrahepatic Insulin Clearance.* Hepatic and peripheral insulin clearances were estimated using a model for insulin kinetics during the FS-IVGTT as described in Fig. 3.

The model is based on the following main assumptions:

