- **CCT, OGTT and HCG-ST** – The major risk associated with these tests is insertion of an intravenous catheter for blood drawing as discussed above. Glucose ingestion during the OGTT may cause abdominal discomfort, nausea, increased blood pressure, flushing or sweating. Dairy cream ingestion may cause urticaria, pruritus and in rare cases anaphylaxis in individuals with an unknown dairy allergy; and much less often may cause nausea, cramps, flatulence, bloating or diarrhea in individuals with previously unknown lactose intolerance.
- **FS-IVGTT** – The major risk of this test is hypoglycemia associated with the insulin infusion along with the risk associated with insertion of intravenous catheters for the infusions and blood drawing as discussed above. The frequent glucose measurements will allow prompt detection of hypoglycemia, in which case the test will be stopped and the intravenous glucose infusion will be increased or glucose will be given orally for resolution.
- **DEXA scans** involve a very small amount of radiation. One of the risks associated with radiation exposure is cancer. The natural incidence of fatal cancer in the U.S. is about 1 chance in 5. Everyday radiation exposure from natural occurring background radiation (sun, radon exposure in the home) is approximately 100 mrem (1 mSv) per year. Each subject in this study will receive a whole body DEXA scan. The radiation dose of one whole body DEXA scan is approximately ≤ 0.3 mrem. This amount of radiation is very low as to make an accurate risk estimate meaningless. A negative urine pregnancy test must be documented prior to undergoing the DEXA scan.
- **HCG Administration** – HCG use can cause the following adverse effects: edema, depression, fatigue, headache, irritability, restlessness, ovarian cyst rupture, reaction or pain at the injection site, or a local or systemic hypersensitivity reaction.

The risk of cyst rupture will be minimized by administering the HCG between days 3 and 13 following the onset of either a spontaneous or progestin-induced withdrawal bleed, or without regard to the onset of menses if vaginal sonography within 21 days of HCG administration reveals no evidence of follicle cyst development in the face of a negative pregnancy test.

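### The hypoglycemia row in section 11.0 schedules no glucose reading against the 70 mg/dl limit for the last 60 to 80 minutes of the 240-minute FS-IVGTT (minor)

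*Combined protocol and SAP*

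**What the plan says.** All references are to the combined protocol and SAP.

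- **Check schedule (section 11.0, anticipated risks table, hypoglycemia row).** Glucose is read every 1 to 10 minutes for an initial 1.5 hours, "starting 20 minutes before the test, then every 20-30 minutes for the next 1½ hours". The action in the same row is triggered by symptoms or by glucose below 70 mg/dl.
- **Test length and draws (section 6.1, Insulin-Modified FS-IVGTT).** Time zero is about 8 AM. The sampling list ends "80, 90, 100, 120, 150, 180 and 240 minutes", and "All infusions will be stopped at 12 PM". Insulin is a single 60-second dose at 20 minutes. Plasma is frozen for later assay of glucose and the other analytes, and section 6.6 says that each subject's samples are assayed together at the end of the study.
- **Reliance on readings (section 7.0, FS-IVGTT).** Hypoglycemia is named as the major risk of this test, and "The frequent glucose measurements will allow prompt detection of hypoglycemia".
- **Response, section 7.0.** "the test will be stopped and the intravenous glucose infusion will be increased or glucose will be given orally for resolution". No threshold is given.
- **Response, section 11.0.** The infusions are ceased and intravenous glucose is given, on symptoms or below 70 mg/dl. Oral glucose is not mentioned.
- **Glucose dosing (section 6.1).** "A glucose solution (0.3 gm/kg) will be administered intravenously beginning immediately after the 0 minute blood draw". No continuing glucose infusion is described. The only fluid described as running throughout is saline at 30 cc/hr, in the thrombosis row of the same risk table.

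**The concern.** The plan relies on measured glucose for early detection of the test's main hazard and ties one of its two triggers to a number. A numeric trigger works only while readings are taken. Once the scheduled checks end, a participant who falls below 70 mg/dl without symptoms meets no planned reading, although she is still fasting and the test is still running. The 240-minute draw does not close this as written, because the text describes that plasma only as stored for later assay and the section 11.0 schedule has already ended.

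There is also a smaller wording problem. Staff who act on a low reading find two instructions. One has no threshold and refers to increasing a glucose infusion that the procedure does not describe. The other has a threshold but omits the oral route.

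**Working it through.** This is clock arithmetic on the stated schedule. No power or sample-size figure is involved.

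**Inputs**
- Phase 1 is 90 minutes and phase 2 is 90 minutes (section 11.0 hypoglycemia row).
- The test runs from 0 to 240 minutes: 8 AM to 12 PM is 4 × 60 = 240 (section 6.1; Table 1 gives the same end).
- Insulin is given at 20 minutes (section 6.1).
- There are 34 draws of 8 ml (section 6.1).

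**Check on the sampling list.** The plan states: "A total of 272 ml of blood (8 ml/sample) will be collected during the entire procedure". Counting the listed times gives 34, and 34 × 8 = 272 ml, so the list is complete as printed.

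**End of the scheduled checks, on both readings of the clock**

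| | Clock from 0 | Clock from -20 |
|---|---|---|
| Phase 1 ends | 0 + 90 = +90 | -20 + 90 = +70 |
| Phase 2 ends | 90 + 90 = +180 | 70 + 90 = +160 |
| Time left to 240 | 240 - 180 = 60 min | 240 - 160 = 80 min |
| Share of the 240 min | 60/240 = 25% | 80/240 = 33% |
| Checks after insulin at +20 | 180 - 20 = 160 of 220 min (73%) | 160 - 20 = 140 of 220 min (64%) |
| Listed draws after the schedule ends | 1 of 34 (240) | 2 of 34 (180, 240) |

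Counting from -20 is the more literal reading of the row. Counting from 0 fits the draws better. Their spacing is at most 10 minutes up to +100, then 20 minutes (100 to 120), 30 (120 to 150), 30 (150 to 180) and 60 (180 to 240). Neither fit is exact, since the 10-minute spacing runs to +100 rather than to +90 or +70. The row is best taken as an approximate summary of the draws, and the result as a range. No reading of it reaches +240.

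**Exposure.** Ninety women tested before and after treatment make 90 × 2 = 180 tests. Section 12.2 allows up to 113 patients. If the additional 23 had only the baseline test, the count would be 180 + 23 = 203. These are counts of tests, not of expected events.

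**The two response texts side by side**

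| | Section 7.0 | Section 11.0 |
|---|---|---|
| Trigger | hypoglycemia, no value | symptoms or below 70 mg/dl |
| Stop | the test | the infusions |
| Treat | increase IV glucose, or oral | IV glucose |

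**The case against.** The strongest case against is that the late part of the test is already protected. Section 11.0 requires continuous monitoring for the whole visit and places the principal investigator in the hospital. Section 6.2 keeps a trained person at the bedside. Symptoms alone trigger treatment, and both catheters stay in until the test is complete. Insulin is one short dose at 20 minutes, so dense early checks that taper later are a defensible design. Section 11.0 also makes hypoglycemia during this test a specific item for the DSMB. All of this stands, and it is why the point is minor. What it does not supply is a planned reading for a low value without symptoms.

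It is also fair to say that an immediate 240-minute reading would not be enough by itself. It comes when the test is over and would leave 180 to 240 minutes unread. The fix must include a reading inside that window.

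The documents do not support four stronger inferences that a reader might draw:
- *The last hour is unmonitored.* Only the scheduled glucose readings stop; observation does not.
- *The two response texts contradict each other.* They mostly reconcile as stop and give glucose. A threshold in one place does not conflict with silence in the other, and oral glucose is an added option. What remains is the reference to an infusion being increased. The listed appendix on infusion preparation is not in the text reviewed, so even this is limited to what section 6.1 shows.
- *Late hypoglycemia is likely on salsalate.* Section 2.0 says that the drug raises circulating insulin by reducing hepatic clearance. That is a reason to carry checks through, but no document gives a rate or timing of late low values.
- *The insulin sensitivity endpoint is affected.* Nothing here bears on power, type I error or the analysis models.

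**Conclusion.** The point holds as a minor safety-text gap. The section 11.0 schedule stops at about +160 to +180 minutes and leaves the last 60 to 80 minutes of a 240-minute test without a scheduled reading against the plan's own 70 mg/dl limit. This assumes that the row means what it says about duration and that no document outside the supplied text, such as a bedside procedure sheet, already requires late readings. The size is a length of time without scheduled readings; it is not an estimate of harm. The difference between the two response texts is a secondary wording matter.

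**What to change.** 1. **Extend the hypoglycemia row in section 11.0** to the end of the test, with readings every 30 minutes to 240 minutes. This covers the 180-minute draw on either reading of the clock. It adds a bedside-size glucose reading at about 210 minutes from the existing sampling catheter and an immediate reading of the 240-minute sample before the catheters are removed.
2. **Use one response text in sections 7.0 and 11.0:** on symptoms or glucose below 70 mg/dl, stop the test and give intravenous or oral glucose. The treatment dose stays with the sponsor.

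**Cost.** The 240-minute reading uses blood already drawn and loses no data, because it is the last draw. The 210-minute reading is one very small extra sample. If it were taken as a full study draw, the count would become 35 × 8 = 280 ml. The three tests per period would go from 64 + 330 + 272 = 666 ml to 674 ml, under a ceiling of 750 ml (section 7.0) that other draws share. A bedside-size sample is therefore preferable. A low value at 210 minutes would stop the test before the 240-minute draw, as the plan's own rule already does at earlier times. No extra staff or procedure is needed.
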